8.4 Missing Measurements

For determination of renal response, handling of missing values is addressed in [Section 8.2](#). For the analysis of individual components of other outcome research endpoints (Adult: SF Physical Function v1.2 8b, SF Fatigue v1.0 Adult 8a and SF Pain Interference v1.0 Adult 8a, Pediatric: SF Physical Function - Mobility v1.0 Peds 8a, SF Fatigue v1.0 Peds 10a and SF Pain Interference v1.0 Peds 8a), other efficacy measures and biomarkers, missing values will not be imputed. See the Safety Analysis Guidelines and Safety Data Conventions for the CTLA4IG program (Referenced earlier) for conventions related to the handling of missing or partial dates and the determination of appropriate default values in such cases and in particular for concomitant medication dose start-dates and end-dates and AE onset dates. All of these rules also apply when deriving efficacy data sets.

8.5 Multiple Measurements

When lab samples are inadvertently taken or analyzed multiple times, this produces multiple measures for the same date (and time in the case of labs) for the same subject.

In such cases, the average of such multiple assessments or lab results will be used for this time point for this subject.

When clinical measurements are assessed multiple times at the same date for the same subject, the record with the latest ‘last change time stamp’ will be used for this time point for this subject.

8.6 Day Ranges for Analysis Time Points

Subjects do not always adhere strictly to the visit schedule timing in the protocol. Therefore the designation of visits during treatment will be based on the day of evaluation relative to the study (day of first infusion = study Day 1) rather than the nominal visit recorded in the case report form (CRF). Mutually exclusive relative day windows are defined in the following table to provide derived visits that correspond to the post-baseline time points specified in the protocol.

Designation of visits for efficacy assessments and outcomes research performed at every scheduled visit is tabulated in [Table 8.6-1](#).

Table 8.6-1: Day Ranges for Components of Renal Response, Component of Completed Remission and Outcomes Research Assessments at Every Scheduled Visit During the Double-Blind Period and OLE Period

Visit	Target Day	Component of Renal Response/ Complete Remission (UPCR, eGFR)	eGFR (Provided by Lab)	Outcomes Research Day Ranges
Double-blind period				
Screening	< 1	< 1	< 1	< 1
Day 1 (Baseline)	1	1	1	1
Day 15	15	8 - 22		
Day 29	29	23 - 43		
Day 57	57	44 - 71		
Day 85	85	72 - 99		2 - 99
Day 113*	113	100 - 127	50 - 177	100 - 127
OLE period				
Day 141	141	128 - 155		
Day 169	169	156 - 183		
Day 197	197	184 - 211		
Day 225	225	212 - 239		
Day 253	253	240 - 267		
Day 281	281	268 - 295		

* Day 113 assessment for subjects continuing in OLE, the upper inclusive limit of this window is the first infusion in OLE or 42 days after last dose in double-blind period, whichever comes earlier. Assessments within 42 days after last dose in double-blind period are included for subjects discontinuing during double-blind period.

For subjects who completed Period 1 and entered Period 2 prior to the protocol revision:

Table 8.6-2: For Subjects who Completed Period 1 and Entered Period 2 prior to the Protocol Revision

Visit	Target Day	Component of Renal Response/ Complete Remission (UPCR, eGFR)	eGFR (Provided by Lab)	Outcomes Research Day Ranges
Double-blind (Period 1 and Period 2)				
Screening	< 1	< 1	< 1	< 1

Table 8.6-2: For Subjects who Completed Period 1 and Entered Period 2 prior to the Protocol Revision

Visit	Target Day	Component of Renal Response/ Complete Remission (UPCR, eGFR)	eGFR (Provided by Lab)	Outcomes Research Day Ranges
Day 1 (Baseline)	1	1	1	1
Day 15	15	8 - 22		
Day 29	29	23 - 43		
Day 57	57	44 - 71		
Day 85	85	72 - 99		2 - 99
Day 113*	113	100 - 120	50 - 141	100 - 127
Day 128	128	121 - 134		
Day 141	141	135 - 155		
Day 169	169	156 - 183-	142 - 183	
Day 197	197	184 - 211	184 - 211	
Day 225*	225	212 - 239	212 - 239	
OLE period				
Day 253	253	240 - 267		
Day 281	281	268 - 295		
Day 309	309	296 - 323		
Day 337	337	324 - 351		
Day 365	365	352 - 379		
Day 393	393	380 - 407		

* Day 113 assessment for subjects continuing in Period 2, the upper inclusive limit of this window is the first infusion in Period 2 or 42 days after last dose in Period 1, whichever comes earlier. Day 113 assessment extends 42 days after last dose in Period 1 for subjects discontinuing during Period 1. Similarly, Day 225 assessment for subjects continuing in OLE, the upper inclusive limit of this window is the first infusion in OLE or 42 days after last dose in Period 2, whichever comes earlier. Assessments within 42 days after last dose in Period 2 are included for subjects discontinuing during Period 2.

Table 8.6-3: Day Ranges for Laboratory Assessments at Every Scheduled Visit During the Double-Blind Period and OLE Period

Visit	Target Day	Chemistry	CBC	Total Cholesterol and Triglycerides, fasting
Double-blind period				
Screening	< 1	< 1	< 1	< 1
Day 1 (Baseline)	1	1	1	1

Table 8.6-3: Day Ranges for Laboratory Assessments at Every Scheduled Visit During the Double-Blind Period and OLE Period

Visit	Target Day	Chemistry	CBC	Total Cholesterol and Triglycerides, fasting
Day 15	15	8 - 22		
Day 29	29	23 - 43	15 - 57	
Day 57	57	44 - 71		28 - 56
Day 85	85	72 - 99	58 - 99	
Day 113*	113	100 - 141	100 - 197	57 - 197
OLE period				
Day 169	169	142 - 197		
Day 225	225	198 - 253		
Day 281	281	254 - 309	198 - 309	198 - 309

* Day 113 assessment for subjects continuing in OLE, the upper inclusive limit of this window is the first infusion in OLE or 42 days after last dose in double-blind period, whichever comes earlier. Assessments within 42 days after last dose in double-blind period are included for subjects discontinuing during double-blind period.

For subjects who completed Period 1 and entered Period 2 prior to the protocol revision:

Table 8.6-4: For Subjects who Completed Period 1 and Entered Period 2 prior to the Protocol Revision

Visit	Target Day	Chemistry	CBC	Total Cholesterol and Triglycerides, fasting
Double-blind (Period 1 and Period 2)				
Screening	< 1	< 1	< 1	< 1
Day 1 (Baseline)	1	1	1	1
Day 15	15	8 - 22		
Day 29	29	23 - 43	15 - 57	
Day 57	57	44 - 71		28 - 56
Day 85	85	72 - 99	58 - 99	
Day 113*	113	100 - 120	100 - 141	57 - 169
Day 128	128	121 - 134		
Day 141	141	135 - 155		
Day 169	169	156 - 183-	142 - 197	
Day 197	197	184 - 211		
Day 225*	225	212 - 253	198 - 309	170 - 309
OLE period				

Table 8.6-4: For Subjects who Completed Period 1 and Entered Period 2 prior to the Protocol Revision

Visit	Target Day	Chemistry	CBC	Total Cholesterol and Triglycerides, fasting
Day 281	281	254 - 309		
Day 337	337	310 - 365		
Day 393	393	366 - 421	310 - 421	310 - 421

* Day 113 assessment for subjects continuing in Period 2, the upper inclusive limit of this window is the first infusion in Period 2 or 42 days after last dose in Period 1, whichever comes earlier. Day 113 assessment extends 42days after last dose in Period 1 for subjects discontinuing during Period 1. Similarly, Day 225 assessment for subjects continuing in OLE, the upper inclusive limit of this window is the first infusion in OLE or 42 days after last dose in Period 2, whichever comes earlier. Assessments within 42 days after last dose in Period 2 are included for subjects discontinuing during Period 2.

Table 8.6-5: Day Ranges for Immunogenicity Assessments at Every Scheduled Visit During the Double -Blind Period and Follow-Up Period

Visit	Target Day	Immunogenicity Day Ranges*
Double-blind period		
Day 1 (Baseline)	1	≤ 1
Day 113	113	8 - 169*
Follow-up period		
Day 56	56	1 - 70
Day 84	84	71 - 126
Day 168	168	127 - 168

* For Day 113 assessment, the upper inclusive limit of this window is the first infusion in OLE or 56 days after last dose in double-blind period, whichever comes earlier.

For subjects who completed Period 1 and entered Period 2 prior to the protocol revision:

Table 8.6-6: For Subjects who Completed Period 1 and Entered Period 2 prior to the Protocol Revision

Visit	Target Day	Immunogenicity Day Ranges*
Double-blind period		
Day 1 (Baseline)	1	≤ 1
Day 113	113	8 - 169*
Day 225	225	170 - 281
Follow-up period		
Day 56	56	1 - 70
Day 84	84	71 - 126
Day 168	168	127 - 168

*For Day 113 assessment, the upper inclusive limit of this window is the first infusion in Period 2 or 56 days after last dose in Period 1, whichever comes earlier

If a subject has more than one visit where a measurement is recorded within a window, the measurement closest to the target day will be used. In case of two visits being equidistant from the target, the later measurement will be used in the analyses. Exceptions to these rules apply to immunogenicity, where the least favorable value (toward a positive response) in the window will be used.

For subjects who discontinue from study therapy prematurely, assessments performed after the last infusion of study drug will be included in the efficacy and safety data sets provided that these assessments are made within 42 and 56 days respectively of the last infusion.

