Eligibility will be based on specified inclusion and exclusion criteria, medical history, disease activity and safety assessments. Randomization should occur within 28 days of signing the informed consent. This may be extended to 42 days to allow for screening results (eg, TB, *APOL1* SNP, UPCR and eGFR).

3.1.2 Double-Blind Period (Day 1 - Day 113):

On Day 1, subjects will be randomized to one of two blinded parallel treatment arms in a 1:1 ratio:

Abatacept IV

adults use weight-tiered dose:

< 60 kg:	500 mg
60 to 100 kg:	750 mg
> 100 kg:	1000 mg

pediatric patients 6 to 17 years:

< 75 kg:	10 mg/kg
≥ 75 kg	follow adult dosing.

Placebo (Normal Saline or D5W following the same dosing schedule).

Dosing is on Day 1, 15, 29, and then every 28 days.

The duration of the Double-Blind Period is 113 days.

There is an option to Early Escape into the OLE on Day 85 for pediatric age subjects only (< 18 years of age at randomization). The decision to Early Escape will be based on the Day 57 UPCR (> 3) and the assessment of clinical status on Day 85. If at the discretion of the investigator, in consultation with the subject (and their guardians), it is decided that the subject's clinical status has worsened or not improved sufficiently based on both of these criteria, the Day 85 visit may be skipped. The subject would complete the Double-Blind Period Early Termination visit ([Table 5.1-2](#)). The decision will then be made to either proceed to the OLE Day 1 visit ([Table 5.1-3](#)) or the Follow-up Visits ([Table 5.1-4](#)).

3.1.3 Open Label Extension (Day 1 - Day 169):

At the end of the Double Blind, there will be a 169 day open label extension (OLE). Subjects may enter this extension in 2 different manners. Subjects who reach the end of Double Blind will be able to volunteer to enter the OLE at the discretion of the investigators. Pediatric age subjects (6 to 17 years) who choose to Early Escape may then choose to enter the OLE. This includes both responder and non-responders who wish to determine if a longer exposure to abatacept could lead to a response. Abatacept will be administered every 28 days starting on Day 1 of the OLE (Day 1 of the OLE will be Day 113 of the Double Blind Treatment Period), without a loading dose. Adjustment in background therapy is allowed but limited. This includes increases or decreases in doses, including discontinuation, or change from one permitted agent to another (3.4.1.2, Restricted Treatments During Double-Blind).

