6 STUDY PERIODS, TREATMENT REGIMENS AND POPULATIONS FOR ANALYSES

6.1 Study Periods

In this study, there are four study periods: screening period, double-blind period (DB), open label extension period (OLE), and follow-up period.

The following analysis periods defined below are for analysis purposes. The definitions below indicate the data to be included in the analysis of each specified period. Subjects discontinued during a specified period (DB or OLE) will be considered on-treatment for 56 and 42 days after the last dosing in that period for safety and efficacy analysis respectively. Follow-up period data will be included in one of the analysis periods depending on the time of completing the study.

Screening Period: Starts with the day of enrolment and ends prior or on the day of first dose of study medication (abatacept or placebo).

Double-Blind Period: Starts with the first dosing of double-blind study medication and ends 56/42 days (for safety/efficacy analysis) after the last dose of the double-blind period or the first dosing of OLE, whichever is earlier.

For subjects who completed Period 1 and entered Period 2 prior to Protocol Amendment 2, includes data from first dose date in Period 1 up to the first dose in Period 2.

Open Label Extension Period (OLE): Starts with the first dosing in the OLE and ends 56/42 (for safety/efficacy analysis) days after the last dose in the OLE.

Cumulative Abatacept Safety Period: Starts at the time of the first dose of abatacept (either in the double-blind period for the subjects randomized to abatacept or in the OLE for the subjects randomized to placebo) and continues up to 56 days post last dose of abatacept for safety (AE and laboratory summaries). The last abatacept dose can be last dose in double-blind period for subjects not treated in the OLE.

For subjects who completed Period 1 and entered Period 2 prior to the protocol revision:

- For subjects on abatacept during Period 1:
 - For subjects who do not enter OLE period: starts with the first dosing of Period 1 and ends 56 days after the last dosing of Period 1.
 - For subjects who enter OLE period: starts with the first dosing of Period 1 and ends 56 days after the last dosing of Period 1 combined with OLE period that starts with the first dosing in the OLE period and ends 56 days after the last dosing in the OLE period.
- For subjects on placebo during Period 1:

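### SAP Table 8.6-1 assumes an open-label start near Day 113, so the OLE Day 29 UPCR of a child who escapes at Day 85 falls in no analysis row (minor; descriptive outputs only)

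*SAP*

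**What the plan says.** **The clock.** SAP 8.6 assigns every visit by study day: "visits during treatment will be based on the day of evaluation relative to the study (day of first infusion = study Day 1"). The stated aim is "to provide derived visits that correspond to the post-baseline time points specified in the protocol".

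**The OLE rows.** Table 8.6-1 gives UPCR targets 141, 169, 197, 225, 253 and 281, the first with window 128-155 and the last with 268-295. Table 8.6-3 ("Day Ranges for Laboratory Assessments at Every Scheduled Visit During the Double-Blind Period and OLE Period") gives chemistry rows 142-197, 198-253 and 254-309, and one OLE row, 198-309, for CBC and lipids.

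**Where the double-blind rows stop.** For subjects continuing into the OLE, the footnote to the Day 113 row says that "the upper inclusive limit of this window is the first infusion in OLE or 42 days after last dose in double-blind period", taking the earlier. SAP 6.1 likewise ends the double-blind period a fixed number of days (42 for efficacy) "after the last dose of the double-blind period or the first dosing of OLE, whichever is earlier".

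**The other entry route.** Protocol 3.1.2 states: "There is an option to Early Escape into the OLE on Day 85 for pediatric age subjects only". Footnote a of Protocol Table 5.1-2 makes Day 85 the Early Termination visit for these children, and Table 5.1-3 puts OLE Day 1 on the same day as the last double-blind visit. Protocol 3.1.3, however, says without exception that "Day 1 of the OLE will be Day 113 of the Double Blind Treatment Period".

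**Who gets separate tables.** Tables 8.6-2 and 8.6-4 are introduced with "For subjects who completed Period 1 and entered Period 2 prior to the protocol revision" and carry OLE rows for a start at Day 225. No table covers a start at Day 85. In the readable SAP, early escape appears only in the amendment table of section 2.4.

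**The concern.** The SAP incorporates the amendment that created early escape and gives former Period 2 subjects their own windows, yet its windows do not cover the Day 85 entry that the same amendment introduced. Applied as written, they drop a scheduled post-baseline UPCR from a planned summary. For a placebo-arm escaper that value is the first scheduled UPCR after the first abatacept dose.

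The outputs at stake are:
- the descriptive UPCR and albumin change summaries over the OLE (SAP 7.5.3 and 9);
- the all-period UPCR graphs (SAP 7.5.3);
- the chemistry shift tables planned for the OLE (SAP 7.6.5 and Table 9-2).

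**Working it through.** **Inputs.** OLE UPCR visits are OLE Days 29, 57, 85, 113, 141 and 169; chemistry is at 57, 113 and 169; CBC and lipids are at 169; visits are allowed ±7 days (Protocol Table 5.1-3). Windows are those of SAP Tables 8.6-1 and 8.6-3.

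**Formula.** Study day = OLE start day + OLE day − 1.

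**Reproducing the plan's targets.** With a start at Day 113, 113 + 29 − 1 = 141, and the later visits give 169, 197, 225, 253 and 281. These are exactly the Table 8.6-1 targets.

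**UPCR with a start at Day 85.**

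| OLE day | Study day (±7) | Row reached | Completers' OLE day in that row |
|---|---|---|---|
| 29 | 113 (106-120) | none | – |
| 57 | 141 (134-148) | Day 141 | 29 |
| 85 | 169 (162-176) | Day 169 | 57 |
| 113 | 197 (190-204) | Day 197 | 85 |
| 141 | 225 (218-232) | Day 225 | 113 |
| 169 | 253 (246-260) | Day 253 | 141 |

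Each result holds on all 15 permitted visit days. No on-schedule escaper reaches the Day 281 row.

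**Why the Day 113 row cannot take the first value.** It spans 100-127 but closes at the first OLE infusion, here Day 85, before it opens. If the Day 85 double-blind dose is skipped, the other limit is Day 57 + 42 = Day 99, also below 100.

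**Sensitivity to the start day.** On-schedule UPCR visits line up with completers only if start + 28 lies in 128-155, that is, for starts on Days 100 to 127. Suppose the escape start varies over Days 78 to 92 (an assumption taken from the ±7 day window). Then none of the 15 start days qualifies. OLE Day 29 falls on study Days 99 to 127, and none of the 225 start-by-visit combinations reaches an OLE row. One combination lands on Day 99, inside the Day 85 row, and is kept out only by SAP 6.1.

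**Time since first abatacept in the Day 141 row.** In the abatacept arm, escapers and completers are both at 141 − 1 = 140 days. In the placebo arm, escapers are at 141 − 85 = 56 days and completers at 141 − 113 = 28 days.

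**Chemistry (Table 8.6-3), start exactly at Day 85, on schedule.**
- OLE Day 57 is study Day 141. The first OLE row opens at 142 and the double-blind row is closed, so the value has no row.
- OLE Day 113 is Day 197, which falls in the Day 169 row with completers' OLE Day 57: 113 − 57 = 56 days apart.
- OLE Day 169 is Day 253, which falls in the Day 225 row with completers' OLE Day 113: 169 − 113 = 56 days apart.

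Study Days 141, 197 and 253 are all upper limits of their windows. With a start at Day 86 all three visits line up, and on-schedule alignment holds for starts on Days 86 to 141. That covers 7 of the 15 assumed start days.

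**CBC and lipids.** OLE Day 169 is study Day 253, inside 198-309. This is the completers' own row.

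**The case against.** **Pooling reflects a choice of time axis.** This stands. The SAP states its clock openly, the study-day labels are true, and change is measured from study baseline. Study-day rows align total abatacept exposure in the abatacept arm; OLE-day rows align time since first abatacept in the placebo arm. Each axis misaligns one arm by 28 days. A reader might infer that the shared rows are in themselves an error that biases the results, but the documents do not support that. Nor does the descriptive UPCR summary say it is split by arm; only the albumin summary does. The missing row is a different matter, because neither axis justifies dropping a scheduled value.

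**The 28-day figure is not general.** A reader might carry it over to Table 8.6-3. It holds for UPCR only; chemistry shows either 56 days or no misalignment, depending on one day.

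**Protocol 3.1.3 puts OLE Day 1 at Day 113.** Read literally for everyone, this would remove the gap. It conflicts, however, with the Day 85 escape route and with the same-day rule in Table 5.1-3. The conflict has to be reconciled and cannot be taken as an answer.

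**A rule may sit in redacted text.** SAP 7.5 refers to a section 7.5.4 that is not readable. A rule for escapers could be there, so the finding rests on the readable text.

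**Little is at stake.** This stands too. SAP 7.5 places the efficacy focus on the double-blind period, and the closeout report is mainly about safety. The counts of 15 and 225 enumerate calendar days and do not measure impact.

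**Conclusion.** The gap is real and minor. With an OLE start at Day 85 and visits within ±7 days, the written windows leave one of six OLE UPCR values per escaper without a row. Chemistry is a boundary effect, and CBC and lipids are unaffected.

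A reader might infer that the primary result is at risk. It is not. Closing the Day 113 row at the first OLE infusion keeps open-label values out of it, and SAP 7.5.1 and 8.2 already count discontinued subjects and those without Day 113 data as non-responders. An open-label value could enter that row only if the footnote were not programmed.

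The conclusion assumes that escapers start the OLE at or near Day 85 and that no redacted rule covers them. The documents do not give the number of escapers, which may be zero, so neither the size nor the direction of any shift in a row mean can be stated.

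**What to change.** Define the OLE windows by OLE day, stating that the first OLE infusion is OLE Day 1:

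- UPCR: 16-43, 44-71, 72-99, 100-127, 128-155, 156-183 (targets 29, 57, 85, 113, 141, 169).
- Chemistry: 30-85, 86-141, 142-197 (targets 57, 113, 169).
- CBC and lipids: 86-197 (target 169).

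These are the printed limits minus 112 (for example, 128 − 112 = 16 and 155 − 112 = 43), so subjects who start at Day 113 do not move. They also equal the OLE limits of Tables 8.6-2 and 8.6-4 minus 224 (240 − 224 = 16). Every visit within ±7 days then falls in its own row whatever the start day. Keep the study-day axis for the all-period UPCR graphs.

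At minimum, add a row for escapers' UPCR taken after the first OLE infusion on study Days 100-127. Label it as OLE so that it is distinct from the double-blind Day 113 row. This recovers the missing UPCR value but leaves the shared rows and the chemistry boundary as they are.

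Protocol 3.1.3 and the Day 85 escape route must also be reconciled.

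The cost is SAP table edits and reprogramming of OLE visit labels, with no new data. The downside of the OLE-day axis is that abatacept-arm escapers and completers in the same row differ by 28 days in total exposure; a table footnote should say so.

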7.5.3 Analysis of Secondary Efficacy Endpoints

- Mean change from baseline in UPCR at Day 113: Longitudinal (repeated measure) mixed model will be used to assess this endpoint. The model will include treatment group, UPCR baseline value and randomization stratification factors (genotype and age), time, baseline value by time interaction, time by treatment interaction as fixed effects and subject as a random effect. An unstructured covariance matrix will be used to model the correlation of the repeated measures within each subject. The SAS procedure PROC MIXED will be used with the restricted maximum likelihood (REML) method for estimation and the denominator degrees of freedom will be calculated according to the Kenward Roger method. Adjusted mean change

from baseline by treatment groups and associated standard errors (SE) will be presented as well as treatment differences versus placebo with 95% confidence intervals. A summary will be provided, presenting the mean change from baseline in UPCR at each time point in double-blind period as described above. In addition:

- Summary of mean change from baseline in UPCR at each time point during double-blind period and OLE will be provided. This summary will be descriptive without adjusting for stratification or baseline factors.
- Graphs of median percent change from baseline in UPCR during all periods will be presented.

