- Protein excretion determinations from 24 hour urine collections are considered to be more reliable than those obtained from spot urine collections. This is due primarily to the variability in the protein loss over the course of the day in chronic kidney diseases (CKD). This variability may not be similar between different forms of CKD. To help determine the degree of variability that may exist in subjects with TRNS (FSGS/MCD), UPCR are to be taken from a 24-hour urine collection on Day 1 and 113; if not possible, then from a single voided specimen. To assess the relationship between the two measurements a correlation analysis will be performed between the two measurements as an exploratory analysis. The analysis will be performed if more than 50% of subjects have both 24-hour collection and single voided specimen paired. The correlation between the 24-hour UPCR and single-void UPCR will be examined using the Pearson correlation coefficient or Kendall's Tau if either measure is not normally distributed; the estimate of the correlation coefficient and corresponding 95% CI will be provided; all subjects will be combined into one group for this analysis.
- Mean change from baseline in serum albumin at Day 113. A similar mixed model used in the above secondary endpoint will be applied for this endpoint. Adjusted mean change from baseline by treatment group and associated standard errors (SE) will be presented as well as treatment differences versus placebo with 95% confidence intervals will be provided. A summary will be provided, presenting the mean change from baseline in serum albumin at each time point in double-blind period as described above.
 - Additional summary of mean change from baseline in serum albumin at each time point during OLE will be provided. This summary will be descriptive without adjusting to stratification or baseline factors and will be presented by treatment arm.

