9 CONTENT OF REPORTS

The results of this study will be presented in a standard BMS Clinical Study Report (CSR). Prior to completion of the CSR an Initial Data Assessment will be prepared briefly identifying the key results and any unanticipated findings that are unusual for a study within this program. Prior to completion of the Initial Data Assessment, a meeting for the Initial Data Assessment of study results will be held after database lock and unblinding. Attendees at this meeting will review efficacy and safety summaries and listings and will identify key results that should be highlighted in the Initial Data Assessment and CSR.

At the end of the study, when all subjects complete the follow-up period or discontinue prematurely, a final closeout report will be prepared. The reports will be mainly presenting safety summaries based on the OLE and the cumulative period. It will include the following summaries and the associated listings indicated in the respective sections in this analysis plan:

- Subject Disposition.
- Exposure summaries presented in [Section 7.4](#).
- Efficacy: Changes from baseline in UPCR and serum albumin.
- Adverse Events:
 - Serious adverse events (SAE).
 - AEs leading to study drug discontinuation.
 - AEs related to study drug.
 - Related events categorized by intensity.
 - Most common related AEs (reported in at least 2% of subjects in any treatment group).
 - AEs by intensity.
 - All AEs (serious or non-serious).
 - Most common (serious or non-serious) AEs (reported in at least 5% of subjects in any treatment group).
 - Serious adverse events and related serious adverse events with death as an outcome following EudraCT requirements.
 - Multiple AEs summaries including the required EudraCT summaries in [Section 7.6.4.1](#) (based on cumulative abatacept safety period).
- Laboratory Summaries:
 - Laboratory abnormalities.
 - Shift tables.
- Vital Signs based on OLE period only.
- Immunogenicity.
- Pharmacokinetics.

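### SAP 8.6 has no open-label visit windows for children who escape at Day 85, so their first open-label UPCR reaches no open-label row and, on schedule, later ones sit one row early

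*SAP*

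**What the plan says.** SAP 8.6 assigns visits by "the day of evaluation relative to the study (day of first infusion = study Day 1" and sets the CRF visit label aside. In Table 8.6-1 the OLE rows for UPCR have targets 141, 169, 197, 225, 253 and 281, starting at 128-155 and ending at 268-295. The companion table, "Day Ranges for Laboratory Assessments at Every Scheduled Visit During the Double-Blind Period and OLE Period" (Table 8.6-3), has chemistry rows at 169 (142-197), 225 (198-253) and 281 (254-309), and one OLE row for CBC and lipids at 281 (198-309).

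The Day 113 row runs over 100-127 for UPCR and 100-141 for chemistry. For subjects continuing into the OLE, "the upper inclusive limit of this window is the first infusion in OLE or 42 days after last dose in double-blind period", taking the earlier of the two. When a row holds two values, "the measurement closest to the target day will be used".

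The protocol gives a second way into the OLE. Section 3.1.2 lets subjects under 18 escape on Day 85. Footnote a of Table 5.1-2 makes Day 85 their early termination visit, and Table 5.1-3 puts OLE Day 1 on the day of the last double-blind visit. Protocol 3.1.3 nevertheless equates OLE Day 1 with Day 113.

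SAP 2.4 lists the escape option under Amendment 2, and the SAP's document history says version 2.0 incorporates that amendment. Tables 8.6-2 and 8.6-4 give separate windows to former Period 2 subjects. Nothing equivalent exists for escapers.

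The outputs that use these rows are in SAP 7.5.3: "Summary of mean change from baseline in UPCR at each time point during double-blind period and OLE will be provided"; "Additional summary of mean change from baseline in serum albumin at each time point during OLE will be provided"; "Graphs of median percent change from baseline in UPCR during all periods will be presented". For the closeout report, SAP 9 lists "Efficacy: Changes from baseline in UPCR and serum albumin" as its efficacy content.

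**The concern.** The row an open-label value enters depends on the study day, and the rows are spaced for subjects who start the OLE on Day 113. A child who starts four weeks sooner has every OLE visit four weeks sooner on that clock, so values can fall into a gap or into a row meant for a different visit.

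The subjects affected are selected: Day 57 UPCR above 3 and clinical status judged not good enough (Protocol 3.1.2). A stated reason for the OLE is to see whether longer exposure helps non-responders (Protocol 3.1). Change in UPCR and albumin is the only efficacy content that SAP 9 names for the closeout report. If the first open-label value of these children is missing from the tables and later values sit beside completers at another OLE visit, the open-label time course is harder to read for the group it was meant to describe.

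**Working it through.** **Inputs.** Windows and cap: SAP Tables 8.6-1 and 8.6-3 with footnotes. OLE schedule and ±7-day tolerance: Protocol Table 5.1-3 (UPCR at OLE Days 29, 57, 85, 113, 141, 169; chemistry at 57, 113, 169; CBC and lipids at 169). Double-blind dosing window of ±7 days after Day 29: Protocol 4.5.2. From the last of these I take an escaper's OLE Day 1 to lie on study Days 78 to 92.

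**Formula.** Study day = study day of first OLE infusion + OLE day - 1.

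**The plan's own targets.** With OLE Day 1 on Day 113, study day = OLE day + 112. UPCR falls on 141, 169, 197, 225, 253, 281 and chemistry on 169, 225, 281, which are exactly the tabulated targets. Completers stay in the intended row across the whole ±7 days.

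**Escaper starting on Day 85.** Study day = OLE day + 84.

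| Assessment | OLE day | Completer: study day (row) | Escaper: study day (row) |
|---|---|---|---|
| UPCR | 29 | 141 (141) | 113 (none) |
| UPCR | 57 | 169 (169) | 141 (141) |
| UPCR | 85 | 197 (197) | 169 (169) |
| UPCR | 113 | 225 (225) | 197 (197) |
| UPCR | 141 | 253 (253) | 225 (225) |
| UPCR | 169 | 281 (281) | 253 (253) |
| Chemistry | 57 | 169 (169) | 141 (none) |
| Chemistry | 113 | 225 (225) | 197 (169) |
| Chemistry | 169 | 281 (281) | 253 (225) |
| CBC, lipids | 169 | 281 (281) | 253 (281) |

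**Why the Day 113 row does not catch the first values.** It opens at Day 100 and closes at the first OLE infusion, Day 85 here and Day 92 at the latest, so it is empty. The other limit gives 57 + 42 = Day 99 when the last blinded dose was on Day 57. Treating the child as a double-blind discontinuation also stops at Day 99 for that dose date.

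**Does timing rescue the first UPCR?** Latest possible day: 92 + 28 + 7 = 127, one day before the first OLE row opens at 128. Earliest: 78 + 28 - 7 = 99. Day 99 is numerically inside the double-blind Day 85 row (72-99), but SAP 6.1 ends the double-blind period at the first OLE infusion, and the Day 78 value is closer to target anyway (7 days against 14). No OLE row is reached in any case.

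**Last UPCR row.** Latest possible final UPCR: 92 + 168 + 7 = 267, the last day of the Day 253 row (240-267). No escaper UPCR enters the Day 281 row.

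**Chemistry by start day, visits on time.**
- Start Day 78: Days 134, 190, 246, giving rows none, 169, 225.
- Start Day 85: Days 141, 197, 253, giving rows none, 169, 225.
- Start Day 86: Days 142, 198, 254, giving rows 169, 225, 281.
- Start Day 92: Days 148, 204, 260, giving rows 169, 225, 281.

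With a Day 85 start, the first chemistry visit has no row on 8 of the 15 permitted days (134-141) and enters the Day 169 row on the other 7 (142-148). If only the second visit is a day late (Day 198), it shares row 198-253 with Day 253. The distances to 225 are 27 and 28, so the final value is dropped.

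**Exposure in shared UPCR rows, Day 141 as example, on schedule.** Abatacept arm: escaper 4 + 2 = 6 prior doses, completer 5 + 1 = 6. Placebo arm: escaper 2 doses over 56 days, completer 1 dose over 28 days. The present clock therefore aligns total abatacept in the abatacept arm but not in the placebo arm.

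**The case against.** The best reply is that the effect is small. The OLE summaries are descriptive and unadjusted, SAP 7.5 says the efficacy analysis is mainly about the double-blind period, and SAP 9 describes the closeout report as mainly safety. Escape is optional, paediatric and at the investigator's discretion; there may be few escapers or none, so no shift in any mean can be shown. Study day is also a defensible axis, because it lines up total abatacept in the abatacept arm. All of this stands and limits the weight of the point. It does not explain a promised by-visit value that has no row to go into.

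Four stronger readings are tempting and should be resisted.

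- **That the first open-label albumin is always lost.** A one-day-later OLE start (Day 86) with on-time visits puts all three chemistry values in the intended rows.
- **That the final visit is scattered over three rows.** At study Day 253 UPCR goes to row 253, chemistry to 225, and CBC and lipids to 281. That split is between different parameters, and no OLE output listed in SAP 9 combines them in one row. With a start on Days 86 to 92 and on-time visits it is two rows.
- **That OLE chemistry means are affected in general.** SAP Appendix 3 (Table 9-2) marks mean change in laboratory parameters for the double-blind period only. Among chemistry analytes, only albumin has a stated OLE mean-change summary; the others are touched through shift-table cells.
- **That the efficacy result is at risk.** Subjects without Day 113 data count as non-responders (SAP 7.5.1 and 8.2), and the cap on the Day 113 row correctly keeps open-label values out of it.

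**Conclusion.** The point holds for UPCR without depending on visit timing: for every escaper whose OLE Day 1 lies on Days 78 to 92 and whose visits are within ±7 days, the OLE Day 29 UPCR reaches no OLE row, and no UPCR reaches the Day 281 row. On schedule, 1 of 6 values is lost and five sit one row (28 days) early.

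For albumin and other chemistry it holds conditionally. With OLE Day 1 on or before Day 85 and on-time visits, 1 of 3 values has no row and two sit one row early; with OLE Day 1 on Days 86 to 92 and on-time visits there is no error. CBC and lipids are placed correctly.

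The reach is the descriptive OLE by-visit UPCR and albumin summaries, the all-periods UPCR graph and visit cells of the laboratory shift tables. The primary analysis and the adverse-event tables are unaffected. The effect on any OLE mean cannot be sized, because the documents do not give the number of escapers. It is a gap worth closing before the end-of-study analysis, not a threat to the trial's conclusions.

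**What to change.** Add to SAP 8.6 a rule that, for early escapers, OLE visits are assigned by days from the first OLE infusion (that infusion = OLE Day 1) and then mapped to the matching existing OLE row. The windows are the OLE rows of Tables 8.6-1 and 8.6-3 minus 112 days:

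- UPCR: OLE Day 29 = 16-43, Day 57 = 44-71, Day 85 = 72-99, Day 113 = 100-127, Day 141 = 128-155, Day 169 = 156-183, mapped to rows 141, 169, 197, 225, 253, 281.
- Chemistry: OLE Day 57 = 30-85, Day 113 = 86-141, Day 169 = 142-197, mapped to rows 169, 225, 281.
- CBC and lipids: OLE Day 169 = 86-197, mapped to row 281.

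On schedule, all 6 UPCR and all 3 chemistry values are then kept, and the final visit sits in the Day 281 row throughout.

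Add a footnote to the OLE tables and the UPCR graph: at the same OLE day, abatacept-arm escapers have had 28 days and one dose less abatacept than abatacept-arm completers (4 blinded doses against 5). This is the trade-off of the change, since the study-day clock aligned them.

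The cost is one rule and one footnote in the SAP, with no new visits or data. Three further steps are optional: re-labelling the OLE rows of Tables 8.6-2 and 8.6-4 (subtracting 224 days gives the same OLE-day windows), showing escapers on separate lines by arm, and limiting Day 113 as OLE Day 1 to completers in Protocol 3.1.3. The last would have to go through the revision process in Protocol 9.1.1.
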